### **8.2. Smoking Status Change**

Smoking status at each post-baseline visit in Full Population will be summarised by arm. The participants who do not complete the visit will be regarded as missing at the certain visit.

### **8.3. COPD Disease Progression**

Disease status (healthy, chronic bronchitis, COPD [GOLD I-IV]) at each post-baseline visit in Full Population will be summarised by arm (reflecting baseline disease status). The participants who do not complete the visit will be regarded as missing at the certain visit. The rule for post-baseline COPD disease status is:

1. If post-bronchodilator FEV1(ml)/FVC(ml)  $\geq 70\%$ , the participants will be shown as “FEV1(ml)/FVC(ml)  $\geq 70\%$ ”, otherwise go to step 2;
2. If post-bronchodilator FEV1(ml)/FVC(ml)  $< 70\%$ , the participant will be regarded as COPD patient and the GOLD grade is defined as:  
GOLD 1: FEV1  $\geq 80\%$  of predicted;  
GOLD 2: FEV1  $< 80\%$  but  $\geq 50\%$  of predicted;  
GOLD 3: FEV1  $< 50\%$  but  $\geq 30\%$  of predicted;  
GOLD 4: FEV1  $< 30\%$  of predicted.

## **9. PATIENT REPORT OUTCOME (PRO) AND ACTIVITY**

For the details of the PROs, please refer to [Patient-reported Outcome](#).

### **9.1. CAT score**

A descriptive summary of CAT score at baseline and every planned test and change from baseline of post-baseline will be provided with N(missing), mean, sd, median, Q1, Q3, Minimum and Maximum. Besides the total score, the summary of the following 2 sub-domain will also be provided:

- Cough and sputum: Defined as the sum of items 1 and 2.
- Breathlessness and activity: Defined as the sum of items 4, 5 and 6.

### **9.2. Other PROs and Questionaries**

Summary of SGRQ Total and subscales will be provided by arm.

Summary of mMRC Dyspnea score will be provided by arm.

Summary of CAPTURE score at baseline and V3 will be provided by arm. CAPTURE score category (defined as  $\geq 2$  and  $< 2$ ) will also be provided in the same table.

### **9.3. EXACT and E-RS**

The EXACT and E-RS are questionnaire-based symptom scores. E-RS utilizes 11 respiratory symptom items from the existing and validated 14-item EXACT. The EXACT/E-RS are collected by daily digital diary, the measurements last for 180 days (6 months) from Visit 1 (baseline) and Visit 3 (month 18). Baseline of EXACT/E-RS is defined as the average of D1-D7. The follow up period start from D8, e.g. 1-6 month is defined as up to 180 days from D8, etc.

Frequency of EXACT events will be summarised by 0, 1, more than 2 for 1-6 month and 18-24 month in participants with at least 3 consecutive records, or 7 records. EXACT event is defined as an increase in EXACT score  $\geq 9$  points for 3 days or  $\geq 12$  points for 2 days, above baseline (average in 7-day period). For more details, please refer to [Patient-reported Outcome](#).

#### **9.4. Digital Activities**

Physical activity will be evaluated by daily steps as assessed by a wrist band dispensed at baseline. Participants are required to keep wearing the wrist band for 1 month from Visit 1 (baseline) and Visit 3 (month 18). The data collected extended the 30-day period will be deleted and not included in analysis.

The value of daily step equal to 0 or  $>23,000$  will be regarded as missing.

The summary of daily step is based on the average for each patient, and will be provided for the following 3 periods:

- Baseline: the average of first 7 days.
- Month 1: the average of up to 30 days from study D8.
- Month 18: the average of up to 30 days from Visit 3 (Month 18).

For the 2 post-baseline period (Visit 1 and Visit 3), participants with at least 3 consecutive days non-missing step data, or at least 7 days non-missing step data will be considered as evaluable. A table with number of evaluable patients, and descriptive summary for participants' average steps will be presented. A box plot will be provided.

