Patient reported outcomes: CAT, SGRQ-C and mMRC, CAPTURE

Spirometry (pre- and post-bronchodilator)

- FEV1
- Forced vital capacity (FVC) & Percent Predicted FVC and FEV1/FVC ratio & Percent Predicted FEV1/FVC
- Forced expiratory volume in 6 seconds (FEV6)
- Forced expiratory flow between 25% and 75% of vital capacity (FEF 25-75) & Percent Predicted FEF 25-75, Forced Expiratory Flow 25% (FEF25), Forced Expiratory Flow 50% (FEF50) and Forced Expiratory Flow 75% (FEF75)
- Peak Expiratory Flow (PEF) & Percent Predicted PEF, time to Peak Expiratory Flow (tPEF) and Maximal Mid-Expiratory Flow (MMEF)
- Forced Expiratory Time (FET) and Volume back extrapolation (VEXT)

- FEV1 percent of predicted and reversibility test
  - Reversibility will be assessed at Visit 1 (baseline) by measurement of FEV1 before and 10 to 30 minutes after administration of a short-acting bronchodilator (e.g. 400µg β2-agonist or up to 160µg anticholinergic). Prior to testing, the patients should not have taken inhaled short-acting bronchodilators in the previous six hours, long-acting bronchodilator in the previous 12 hours or sustained-release theophylline in the previous 24 hours.
  - Reversibility will be calculated as follows: % Reversibility =  
$$\frac{\text{Highest post - bronchodilator FEV}_1 - \text{Highest pre - bronchodilator FEV}_1}{\text{Highest pre - bronchodilator FEV}_1} \times 100$$

Collection of blood samples for protocol defined analysis (plasma fibrinogen and hsCRP, total and differential blood cell count)

In addition, the following assessments will be conducted among the Biomarker & Digital sub-cohort participants only:

Blood biomarkers (including serum sRAGE, CC16, IP-10, HbA1c)

Sputum sample collection for protocol defined analyses (microbiome through molecular methods, cytology)

Lung HRCT

Issue and training in use of electronic diary: EXACT questionnaire (start after clinic visit at baseline)

Digital steps (start after clinic visit at baseline)

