## **Patient Report Outcome (PRO) and Activity (Chapter 9)**

The PROs and activities are not only collected by on site visit, and please refer to Protocol schedule of activities for further details.

CAT at each planned visits, including phone call visits, will be summarised.

EXACT and E-RS are collected for 2 period of 180 days after baseline and Month 18. Summary of these 2 questionnaires will be based on the mean score during baseline (defined as study D1-D7), Month 1-6 (defined as up to 180 days from study D8) and Month 18-24 (defined as up to 180 days from Month 18 visit).

Daily steps collected by wrist band is used to stands for physical activity measures. Daily steps are collected for 2 period of approximately 30 days after baseline and Month 18. Summary of daily steps will be based on the participants mean steps during baseline (defined as study D1-D7), Month 1 (defined as up to 30 days from study D8) and Month 18 (defined as up to 30 days from Month 18 visit).

HRCT data will be summarised at baseline and the end of study. In addition, for participants who had exacerbation visits (a pre-defined special unscheduled visit happened after exacerbation observed), the HRCT data of these visits will be summarised and compared with baseline and the end of study.

[figure not shown]

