## 5.3. Baseline Definitions

Unless otherwise specified, the baseline value will be the assessment with a non-missing value at Visit 1.

For EXACT/E-RS score and daily steps, the baseline is defined as the average value of D1-D7.

Unless otherwise stated, if baseline data is missing, no derivation will be performed, and baseline will be set to missing.

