## 17.5. Appendix 5: Derived and Transformed Data

### 17.5.1. General

Multiple Measurements at One Analysis Time Point	
• Mean of the measurements will be calculated and used in any derivation of summary statistics but if listed, all data will be presented.	
Study Day	
• Calculated as the number of days from visit 1:	
• Ref Date = Missing → Study Day = Missing	
• Ref Date < Visit 1 → Study Day = Ref Date – Visit 1	
• Ref Date ≥ Visit 1 → Study Day = Ref Date – Visit 1 + 1	

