**Digital Physical Activity**

- SEDENTARY - Little to no activity monitored. This could be due to minimal movement, sitting, resting, or sleeping.
- ACTIVE - Some activity monitored. A brisk walk could achieve this intensity.
- HIGHLY\_ACTIVE - High activity monitored. Running or speed walking could achieve this intensity.

• Below is a template of how activity information is summarized for site personnel in Rave EDC

CRF Component	Value Format	Calculation	Example Values
Date	Text	Date of log line record	26 MAR 2015
Sync Date/Time	Text	Date and time data was synced to Garmin	26 MAR 2015 14:00
Daily Steps Walked	Numeric	Total # of steps in routine data objects for a subject's day (timezone is subject's)	2240
Sedentary Minutes	Numeric	Total # of minutes in routine data objects for a subject's day (timezone is subject's) with intensity parameter = sedentary	438
% of time sedentary	Numeric	Total # of minutes in routine data objects for a subject's day (timezone is subject's) with intensity parameter = sedentary divided by 1440 minutes (total # of minutes per day)	85.32
Active Minutes	Numeric	Total # of minutes in routine data objects for a subject's day (timezone is subject's) with intensity parameter = active	74
% of time active	Numeric	Total # of minutes in routine data objects for a subject's day (timezone is subject's) with intensity parameter = active divided by 1440 minutes (total # of minutes per day)	14.47
Very Active Minutes	Numeric	Total # of minutes in routine data objects for a subject's day (timezone is subject's) with intensity parameter = very active	1
% of time very active	Numeric	Total # of minutes in routine data objects for a subject's day (timezone is subject's) with intensity parameter = very active divided by 1440 minutes (total # of minutes per day)	0.20

Digital Physical Activity			
Total Daily Minutes Sleep	Numeric	Total # of minutes in sleep data objects for a subject's day (timezone is subject's)	362

Phenotype	
Exacerbator	

 
Exacerbator is categorized based on the number of exacerbations patients have in the past:           
 
Never
 
Occasional (1 in the last 2 years)
 
Yearly (1 each year in the last 2 years)
 
 
 
Frequent (<math>\geq 2</math> in the previous year)
 
	
Chronic mucus hypersecretion (CMH)	

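### The daily-steps baseline week counts the band hand-out day, normally only partly recorded, so baseline steps are biased low and a later decline is understated

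*SAP*

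**What the plan says.** Three places in the SAP define the baseline for steps. SAP 5.3 states: "For EXACT/E-RS score and daily steps, the baseline is defined as the average value of D1-D7". SAP 2.2.1 uses the same study days, and SAP 9.4 words it as "Baseline: the average of first 7 days".

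SAP 17.5.1 fixes what D1 is: "Ref Date ≥ Visit 1 → Study Day = Ref Date – Visit 1 + 1". The Visit 1 date is therefore D1, and SAP 11 also labels Visit 1 as Day 1.

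Protocol 9.1 lists, among the sub-cohort baseline procedures, "Digital steps (start after clinic visit at baseline". SAP 9.4 adds that the wrist band is dispensed at baseline. The template in SAP 17.5.3 totals steps over the participant's calendar day and does not scale them for hours worn.

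The other rules in SAP 9.4 are:
- A daily count of 0 or above 23,000 is set to missing.
- Data beyond the 30-day period are deleted.
- The two post-baseline periods need three consecutive, or seven, non-missing days to be evaluable.
- Month 1 runs for up to 30 days from D8, and Month 18 for up to 30 days from Visit 3.

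**The concern.** Read together, these statements put the hand-out day into the baseline mean although its count begins part-way through the day. A low but non-zero count passes the value filter, and neither the 30-day deletion nor the evaluability rule removes it.

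The three reporting periods do not carry this day equally. It is one of seven days at baseline and absent from Month 1. Month 18 may hold one similar day, the Visit 3 date, in about 30. The resulting error has one direction and does not shrink with sample size.

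Change in physical activity, with daily steps as the measure, is a named sub-cohort endpoint under Objective 1. SAP 9.4 will show the three periods in one table and a box plot, so any shift between them will be read as change in activity. The baseline week also has no minimum number of valid days, so the part-day can carry more than 1/7 of the mean.

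**Working it through.** The documents give no sample size, standard deviation or expected change for daily steps, so there is no figure of the plan's own to reproduce.

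**Inputs from the documents**
- Baseline is D1-D7 (SAP 2.2.1, 5.3) or the first seven days (SAP 9.4).
- D1 is the Visit 1 date (SAP 17.5.1).
- Recording starts after the Visit 1 clinic visit (Protocol 9.1).
- Month 1 starts at D8; Month 18 covers up to 30 days from Visit 3 (SAP 9.4).

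**Assumption**
- f is the share of a usual day's steps recorded on the hand-out day. The documents do not give it, so a range of 0.10 to 0.75 is shown. The same f is used for the Visit 3 day where that day is taken as partial.

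**Formulas, with all days valid**
- Observed over true baseline = (6+f)/7, so the bias is -(1-f)/7.
- Month 1 ratio = 1.
- Month 18 ratio = 1 if the Visit 3 day is complete, or (29+f)/30 if it is partial.
- Apparent change = (1 + true change) × Month 18 ratio ÷ baseline ratio - 1.

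**Results with no true change**

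| f | Baseline ratio | Baseline bias | Apparent Month 18 change, Visit 3 day complete | Apparent Month 18 change, Visit 3 day partial |
|---|---|---|---|---|
| 0.10 | 0.871 | -12.9% | +14.8% | +11.3% |
| 0.25 | 0.893 | -10.7% | +12.0% | +9.2% |
| 0.50 | 0.929 | -7.1% | +7.7% | +5.9% |
| 0.75 | 0.964 | -3.6% | +3.7% | +2.8% |

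At f = 0.5, for example, 1/0.929 = 1.077 and (29.5/30)/0.929 = 1.059. Month 1 against baseline follows the column for a complete Visit 3 day.

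**Results with a true 10% fall, f = 0.5**
- Visit 3 day complete: 0.90/0.929 - 1 = -3.1%.
- Visit 3 day partial: 0.90 × 0.983/0.929 - 1 = -4.7%.

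**Fewer valid baseline days**

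With k valid days including the part-day, the bias is -(1-f)/k. At f = 0.5 it is -8.3% for six days, -16.7% for three and -50% for one.

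**The 30-day statements**

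Thirty days from D8 end at D37. If data beyond D30 are deleted, Month 1 keeps only D8-D30, which is 23 days. SAP 9.4 does not say which applies.

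**The case against.** The strongest reply is that the consequence is limited. The study is mainly descriptive, and SAP 9.4 plans period averages and a box plot, with no change model or test. A model of change in steps appears only in the earlier reporting and analysis plan appended to the SAP. If f is similar across arms, every arm's ratio to baseline is scaled by the same factor, so relative comparisons between arms are largely unaffected. This stands and limits the weight of the point. It does not protect within-arm change, which is the endpoint.

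The part-day is also not established for every participant. A hand-out day with 0 steps is set to missing, and Visit 1 has a +7-day window (Protocol Table 1), so the band may be given after D1. This stands too, but it is not a cure. With a later hand-out, the D1-D7 wording leaves fewer days and gives the part-day more weight, while the first-seven-days wording still counts it as one of seven.

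The evaluability sentence in SAP 9.4 names Visit 1 and Visit 3 in parentheses, so it could be read as covering both wear periods. Even so, it sets no minimum for the seven baseline days themselves.

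A reader might take the example day in SAP 17.5.3 as evidence of poor wear, since 438 + 74 + 1 = 513 of 1,440 minutes are recorded. The documents do not support this. The row is a template for site staff, dated 26 MAR 2015, before the original protocol of 18-OCT-2018. Its sync time is 14:00 on the same day, so at most 14 × 60 = 840 minutes had passed, and sleep minutes are held in a separate field.

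**Conclusion.** The point holds as a bounded bias. The baseline definition admits a day that is normally incomplete, and no first-day rule removes it. With seven valid days, baseline is low by (1-f)/7: 3.6% to 12.9% for f between 0.75 and 0.10, and always less than 1/7 = 14.3%. At f = 0.5, no change appears as +5.9% or +7.7% at Month 18, depending on whether the Visit 3 day is partial. These sizes rest on the assumed f, on full sets of valid days, and on hand-out at Visit 1 with a non-zero count.

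A reader might go further and infer that a later decline is hidden. The documents support only that it is understated. Full masking needs a true decline no larger than the bias: 3.6% to 12.9% over this range of f, or 2.8% to 10.2% if the Visit 3 day is also partial. The documents give neither f nor an expected decline.

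Nor do the documents support a minimum-wear rule built on recorded minutes. SAP 17.5.3 describes sedentary time as little or no monitored activity and does not say that an unworn band is excluded from it.

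The bias is predictable, affects a named endpoint and is cheap to remove, so the SAP should be changed.

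**What to change.** In SAP 2.2.1, 5.3 and 9.4:
- Start the steps baseline on the first full calendar day after the band is dispensed. For hand-out at Visit 1 this is D2-D8, with Month 1 from D9. Use one wording in all three sections, and separate steps from EXACT/E-RS in SAP 5.3, where one sentence now covers both.
- Start Month 18 on the day after Visit 3.
- State a minimum number of valid days for baseline, for example the rule already used for the post-baseline periods.
- Reconcile the Month 1 window of up to 30 days with the deletion of data beyond the 30-day period.

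At f = 0.5, a true 10% fall at Month 18 would then show as -10.0% instead of -3.1% or -4.7%.

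The cost is SAP wording and a programming change on data already captured. Each wear period gives up one day at its start, and the baseline minimum will leave slightly fewer participants evaluable.

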### **10. BIOMAKER ANALYSIS**

Summary of blood biomarkers (plasma fibrinogen, hsCRP, blood cell count, etc.) at each visit will be provided, geometrics mean and standard deviation will be presented in addition to the descriptive statistics (n, mean, standard deviation, median, minimum and maximum).

Summary of additional blood protein analyses (only collected in sub-cohort population) at each visit will be provided in sub-cohort population.

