| Protocol Activity   | Screen/Baseline | Study visit     |   |                 |   |   |
|---|-----------------|-----------------|---|-----------------|---|---|
|   |                 | X  | - | X  | - |   |
| Monthly CAT   | X  | -               | - | X  | - | - |
| Blood biomarkers (inclusive of serum sRAGE, CC16, IP-10, HbA1c) | X               | -               | - | X               | X | X |
| Sputum cytology                                    | X               | -               | - | X               | X | X |
| Sputum microbiome                                  | X               | -               | - | X               | X | X |

CAT=COPD assessment test, COPD=Chronic Obstructive Pulmonary Disease, HRCT=High-resolution computed tomography, EW=Early Withdrawal, EXACT=EXAceration of COPD Tool; SGRQ-C=St.George's Respiratory Questionnaire for COPD. CAPTURE=COPD Assessment in Primary Care to Identify Undiagnosed Respiratory Disease and Exacerbation Risk

1. Exacerbation visits only apply to subjects included in the Biomarker & Digital sub-cohort. Moderate exacerbations are defined as COPD exacerbations that require either systemic corticosteroids (intramuscular (IM), intravenous, or oral) and/or antibiotics. Severe exacerbations are defined as COPD exacerbations requiring hospitalization or result in death.
2. Informed consent must be conducted at the screen visit prior to performing any study procedures.
3. For COPD participants only;
4. When a trimonthly telephone interview overlaps a clinical visit, the COPD exacerbation assessment, COPD medication and treatment questionnaires will be completed at the clinic visit. A month is defined as 30 days in this study.
5. Data collection of COPD exacerbation assessment, COPD medication and treatment are not required for the healthy control participants.
6. CT scan should only be performed at withdrawal visit if the last study CT performed was more than a year ago. Inspiratory and expiratory HRCT scans are required at Visit 1 and Visit 4, while only inspiratory scan will be conducted on exacerbation visit. The CT scan for an exacerbation visit should only be performed if the last study CT scan performed was more than 14 days.
7. Pre-and post- bronchodilator values of spirometry test will be collected at each site visit.

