## **9.3. Exacerbation Visits (sub-cohort only)**

Exacerbation visits only apply to subjects included in the Biomarker & Digital sub-cohort. Exacerbations that occur during the study will be detected through several pathways of reporting, including: direct contact with the study site or using a process of screening questions triggering a site alert and follow-up consultation, at which the investigator will determine whether the worsening of symptoms identified by evening diary meets the definition of a moderate/severe exacerbation and if it does then an exacerbation visit is scheduled. This triggering process is described in Section [9.2.6.2](#). Visit will be scheduled to occur within 72 hours of the alert (symptom onset) ([Figure 4](#)).

At the exacerbation Visit, the following study procedures will be completed: (1) PROs: e.g. the CAT, (2) blood sampling, (3) spirometry, (4) sputum sampling including induced sputum if required, (5) chest imaging, (6) healthcare resource utilization and cost including COPD medication and treatment. The sputum samples must be collected before the subjects receive antibiotics and/or systematic corticosteroids.

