
2. Characterise stable disease and exacerbation phenotypes in China through assessment of blood biomarkers, lung microbiome and radiological features of COPD
	
Main cohort:
 
 
• Plasma fibrinogen and high-sensitivity C-Reactive Protein (hsCRP)
 
• Differential blood cell count (e.g. eosinophils, neutrophils) and haemoglobin
 
 
Additional for sub-cohort
 
 
• Blood biomarkers including but not limited to Serum interferon- <math>\gamma</math> -inducible protein -10 (IP-10), soluble Receptor for Advanced Glycation End Products (sRAGE), Club cell protein (CC16) and HbA1c
 
• Sputum microbiome as assessed by molecular methods
 

Research Questions & Objectives	Endpoints
	
 
• Sputum total differential cell counts and percentage (e.g. total cell count, the counts and percentage of eosinophils and neutrophils)
 
• CCI
 

3. Characterise treatment pathways and healthcare resource utilization and costs in COPD
	
 
• Frequency of treatment with COPD medications; Treatment patterns at the time of study entry and during the study period
 
• Count of outpatient visits, emergency visits, hospitalizations (overall and COPD-specific)
 
• Direct medical costs associated with COPD medications and COPD disease management
 
• Insurance coverage and patient out-of-pocket payment
 

4. Test the feasibility of integrating electronic health records, electronic clinical outcome assessments (eCOA) and physical activity data to support application of digital data analytics (DDA) platform in China studies (e.g. direct digital data capture and integration)
	NA

\*Moderate exacerbations are defined as COPD exacerbations that require either systemic corticosteroids (intramuscular (IM), intravenous, or oral) and/or antibiotics. Severe exacerbations are defined as COPD exacerbations requiring hospitalization (including intubation and admittance to an ICU) or result in death.

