### 17.4.2. Reporting Standards

Reporting Standards	
General	

 
The current GSK Integrated Data Standards Library (IDSL) will be applied for reporting, unless otherwise stated (IDSL Standards Location: https://spope.gsk.com/sites/IDSLLibrary/SitePages/Home.aspx):
 
4.03 to 4.23: General Principles
 
5.01 to 5.08: Principles Related to Data Listings
 
6.01 to 6.11: Principles Related to Summary Tables
 
7.01 to 7.13: Principles Related to Graphics
 
	
Formats	

 
GSK IDSL Statistical Principles (5.03 & 6.06.3) for decimal places (DP's) will be adopted for reporting of data based on the raw data collected, unless otherwise stated.
 
Numeric data will be reported at the precision collected on the eCRF.
 
The reported precision from non eCRF sources will follow the IDSL statistical principles but may be adjusted to a clinically interpretable number of DP's.
 
	
Planned and Actual Time	

 
Reporting for tables, figures and formal statistical analyses : 
 
Planned time will be used in figures, summaries, statistical analyses and calculation of any derived parameters, unless otherwise stated.
 
The impact of any major deviation from the planned assessment times and/or scheduled visit days on the analyses and interpretation of the results will be assessed as appropriate.
 
 
 
Reporting for Data Listings: 
 
Planned and actual time will be shown in listings.
 
Unscheduled or unplanned readings will be presented within the subject's listings.
 
Visits outside the protocol defined time-windows (i.e. recorded as protocol deviations) will be included in statistical analyses.
 
 
 
	
Unscheduled Visits	

 
Unscheduled visits will not be included in summary tables.
 
Unscheduled visits will not be included in figures.
 
All unscheduled visits will be included in listings.
 
	
Descriptive Summary Statistics	
Continuous Data	Refer to IDSL Statistical Principle 6.06.1

Reporting Standards	
Categorical Data	N, n, frequency, %
Graphical Displays	
• Refer to IDSL Statistical Principles 7.01 to 7.13.	

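### SAP section 10 has no clear rule for blood biomarkers at exacerbation visits: read literally they reach listings only, and as an extra visit column they would mix within-person change with who exacerbates

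*SAP*

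**What the plan says.** Objective 2 (SAP 2.2) is to "Characterise stable disease and exacerbation phenotypes in China through assessment of blood biomarkers, lung microbiome and radiological features of COPD". The protocol collects blood for it. Protocol 9.3 states: "At the exacerbation Visit, the following study procedures will be completed: (1) PROs: e.g. the CAT, (2) blood sampling". The protocol's schedule of activities limits who can contribute: "Exacerbation visits only apply to subjects included in the Biomarker & Digital sub-cohort", at most two visits each.

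The planned analysis in SAP section 10 is short. For fibrinogen, hsCRP, cell counts and the like, a summary "at each visit will be provided, geometrics mean and standard deviation will be presented", added to the usual descriptive statistics. For the additional proteins, a summary "at each visit will be provided in sub-cohort population". The section does not mention change from baseline, exacerbation visits, pairing or arm.

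Three other places in the SAP bear on whether exacerbation samples enter those summaries:
- Section 2.2.1 describes the exacerbation visit as "a pre-defined special unscheduled visit happened after exacerbation observed".
- Section 17.4.2 says "Unscheduled visits will not be included in summary tables". The same rule covers figures and sends these visits to listings. Section 17.3.1 bases reporting and analysis on the nominal, scheduled visits.
- Section 6.1, in defining study duration, includes the exacerbation visit among the scheduled visits.

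Imaging is handled differently. SAP section 12 tabulates baseline, exacerbation and end-of-study values in COPD patients scanned at an exacerbation visit, with the changes between them.

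**The concern.** Half of Objective 2 concerns exacerbations, and blood is one of its three named sources of information. For IP-10 the only rationale in protocol 5.4 is as a marker of rhinovirus infection at exacerbation. Yet the SAP does not say how an exacerbation sample is to be used, and its visit labels conflict, so two programmers could follow the text and produce different tables.

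Neither table would serve the objective. One omits the exacerbation values. The other invites comparison of a small selected group with everyone sampled at Visit 1. Protocol 5.4 says that CRP and fibrinogen vary with GOLD stage as well as rising at exacerbation, and it links fibrinogen to exacerbation outcomes. A difference across columns could therefore come partly from the type of participant who exacerbates.

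**Working it through.** No stated figure in the plan is in dispute, so the check is mainly of the text.

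**Step 1. If the exacerbation visit is unscheduled (SAP 2.2.1).** Section 17.4.2 removes it from tables and figures, and 17.3.1 points analysis to scheduled visits. Section 10 contains no exception. The biomarker values remain in listings only.

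**Step 2. If the exacerbation visit is scheduled (SAP 6.1).** Section 10 then gives it a column. The planned numbers behind the columns are:
- Visit 1, fibrinogen, hsCRP and cell counts: all participants, about 2,000.
- Visit 1, sRAGE, CC16, IP-10 and HbA1c: the sub-cohort, 50 + 100 + 100 + 100 + 50 = 400.
- Exacerbation column: only sub-cohort members who had an exacerbation visit. The documents give no expected number.

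**Step 3. What a reader would get by comparing columns in step 2.** Work on the log scale. Let N be the number in the Visit 1 column, m the number of them with an exacerbation sample (one each, for simplicity), t the true mean within-person change, and d the difference in stable level between those m and the rest.
- Exacerbation column mean = base + d + t
- Visit 1 column mean = base + (m/N)d
- Difference = t + (1 − m/N)d

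The second term is not change. It is zero only if d = 0. A within-person contrast in the same m people gives t.

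**Step 4. Illustration.** The values of m, d and t are assumptions; none is in the documents.

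| N | m | d | (1 − m/N)d | Spurious ratio |
|---|---|---|---|---|
| 400 | 80 | 0 | 0 | 1.00 |
| 400 | 80 | 0.10 | 0.080 | 1.083 |
| 400 | 150 | 0.20 | 0.125 | 1.133 |
| 400 | 40 | 0.20 | 0.180 | 1.197 |
| 2,000 | 80 | 0.10 | 0.096 | 1.101 |
| 2,000 | 40 | 0.20 | 0.196 | 1.217 |

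For N = 400, m = 80, d = 0.10 and t = 0.15, the formula gives 0.15 + 0.080 = 0.230. A simulation of 4,000 runs (log SD 0.25, within-person correlation 0.5) gave 0.230 for the unpaired contrast and 0.150 for the paired one.

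**Step 5. Precision.** Those who exacerbate are also in the Visit 1 column, so the two means are correlated. With common variance σ² and within-person correlation ρ:
- Unpaired variance = σ²(1/m + 1/N − 2ρ/N)
- Paired variance = 2(1 − ρ)σ²/m

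Setting these equal gives ρ = 0.5 for any m < N. With m = 100 and N = 350 (assumed), at ρ = 0.5 both are 0.0100σ². At ρ = 0.7 they are 0.00886σ² and 0.0060σ², so the unpaired standard error is √(0.00886/0.0060) = 1.21 times the paired one. Below ρ = 0.5 the unpaired contrast has the smaller variance. The documents give no ρ, so the case for pairing rests on what is estimated.

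**Step 6. Whether another part of the plan fills the gap.**
- SAP 13.2 summarises eosinophils and fibrinogen by threshold but names no exacerbation sample.
- The appended RAP (7.4.1) asks for separate exacerbation-visit analyses of FEV1/FVC and CAT. Its Table 5 does not assign eosinophils or fibrinogen to the exacerbation population.
- Protocol 10.2.2 allows change from baseline at clinic visits where suitable. SAP 8.1, 9.1 and 12 take this up for their own endpoints; section 10 does not.

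**The case against.** The best defence is that the either/or is too strict. The exacerbation visit is a column in the schedule of activities with blood draw marked. SAP section 12 tabulates exacerbation CT despite 17.4.2, so the authors did not treat that rule as absolute. Protocol 10.2.2 could supply a within-person change if an exacerbation visit counts as a clinic visit, and SAP 2.1 does not withdraw that provision. Further phenotype work is openly deferred to post hoc documents, and some relevant text (protocol 10.2.7, one Objective 2 endpoint) is redacted.

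Much of this is fair, and it shows what the sponsor may have intended. It does not settle what section 10 will produce. Section 12 has its own explicit wording for exacerbation visits and section 10 has none. The protocol provision is conditional and is not taken up. Deferral to unspecified later work does not resolve a conflict between three sections of the current SAP. Nothing is inferred here from the redacted text.

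It is also true that section 10 plans no exacerbation-to-stable ratio and that the study is descriptive. The distortion in step 3 is thus in the comparison a reader would draw from the table, not in a planned estimate. Splitting the tables by arm would remove the part due to GOLD grade, but participants who exacerbate may still differ within a grade.

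**Conclusion.** The point stands as a gap and an internal conflict that should be corrected. Under one reading the exacerbation half of Objective 2 has no tabulated blood result. Under the other, the tabulated columns do not compare like with like. The size of the second problem cannot be taken from the documents. With d assumed between 0 and 0.20 and m between 40 and 150, the spurious ratio is 1.00 to 1.20 against the sub-cohort and 1.00 to 1.22 against the full cohort.

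Five stronger conclusions that a reader might draw are not supported:
- That the data are lost. They stay in listings and could be analysed later.
- That those who exacerbate are known to start from higher levels. The protocol links CRP and fibrinogen to GOLD stage and fibrinogen to exacerbation outcomes. It gives no size, and it does not say that stable sRAGE, CC16 or IP-10 is higher in those who exacerbate.
- That every marker is set against 2,000 people. The additional proteins are measured in the sub-cohort only.
- That pairing necessarily narrows the confidence interval. Step 5 shows that this depends on ρ, and no precision gain is claimed.
- That every participant with an exacerbation sample has a Visit 1 sample. One is planned, but sub-cohort membership requires only one additional assessment.

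**What to change.** Reconcile SAP 2.2.1, 6.1 and 17.4.2 by stating that, for biomarkers, exacerbation visits are exempt from the exclusion of unscheduled visits.

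Add one table to SAP section 10, parallel to section 12, in participants with both a Visit 1 and an exacerbation sample. For each marker, give the participant's own baseline, exacerbation and end-of-study (Visit 4 or early withdrawal) values, and the within-participant log-ratio of exacerbation to baseline with a 95% confidence interval. Keep second events and allow for up to two per person when computing the interval, for example by clustering on participant. Present it by arm, including chronic bronchitis, where numbers permit. State how many exacerbation samples lack a Visit 1 pair.

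The cost is a few lines of SAP text and one table. No new data are needed.
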